C.1.b. Impact of a Provider Communication Strategy on Parental Vaccine Hesitancy Towards Childhood Vaccines ([name], Co-I): [name] et al. conducted a cluster RCT of 56 pediatric and family medicine clinics in the greater Seattle metropolitan area to test the effect of a provider communication strategy on parental vaccine hesitancy.²⁸ There were 26 clinics in the control arm in which parents of newborns received usual care and 30 clinics in the intervention arm in which providers received training on a communication strategy called: "Ask, Acknowledge, and Advise." The centerpiece of this strategy was an algorithm in which providers were first encouraged to begin the vaccine recommendation by asking parents what questions they had about the immunization schedule, then acknowledging parental vaccine concerns, and finally, advising parents in a manner specific to their concerns. The intervention training included a well-attended (68% of providers) didactic session at baseline that incorporated videos of providers modeling the communication strategy. Providers in intervention clinics also received paper materials detailing the framework as well as monthly e-mail newsletters and a link to the study website that included a webinar version of the training.

Our primary outcome was the change in the proportion of parents who were VHPs (as measured by the PACV) at recruitment after the birth of their child and follow-up when the child was 6 months old. We found that among all enrolled parents, 11.3% were VHPs. The proportion of VHPs at baseline and follow-up changed

Table 1. PACV-SF: Positive if ≥ 2 hesitant responses

No.	Item	Hesitant Response
1	Have you ever delayed having your child get a shot for reasons other than illness or allergy?*	Yes
2	How concerned are you that a shot might not prevent the disease?	Very concerned, somewhat concerned, or not sure
3	Overall, how hesitant about childhood shots would you consider yourself to be?	Very hesitant, somewhat hesitant, or not sure
4	I trust the information I receive about shots.	Strongly disagree, disagree, or not sure

*Only delay of the birth dose of the hepatitis B vaccine would be relevant for parents of children ≤ 2 months old, as was used and evaluated in a prior study¹⁸

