In a second follow-up study, we assessed whether a participatory format—though associated with decreased vaccine acceptance *after a single visit* compared to a presumptive format—would be associated with increased parental vaccine acceptance *over time*. We conducted a longitudinal prospective cohort study in which we enrolled VHPs (defined as PACV score ≥ 50) of newborns (N=72) prior to their child’s 2 month health supervision visit at Group Health Cooperative (GH), an integrated health care system based in Seattle, WA. After their child’s 2, 4, and 6 month visits, we asked parents what format their child’s provider used to begin the vaccine discussion (categorized as presumptive, participatory, or neither) utilizing a validated instrument for parent self-report of provider initiation format. We used GH records and Washington State Immunization Information System (WAIIS) records to assess child immunization status at 8 months of age and after each visit. We found that exclusive (vs. non-exclusive) use of a participatory format was associated with a child being 37.2% (95% CI: 9.8, 64.6; $P=.009$) more days under-immunized at 8 months of age and visit-specific use of a participatory (vs. presumptive) format was associated with a child being 14% (95% CI: 1.4, 26.6; $P=.03$) more days under-immunized after each visit. **Through these series of projects, we concluded that the presumptive (vs. participatory) communication format for initiating childhood vaccine discussions was positively associated with parental vaccine acceptance and negatively associated with parent visit experience, and that use of a participatory (vs. presumptive) format did not improve vaccine uptake over time.** These studies provide a basis for the PIVOT with MI intervention and demonstrate our expertise in a number of methodological areas relevant to the current proposal including qualitative and quantitative research, measurement of our primary study outcome of days under-immunized, use of immunization registry data, and conducting research within a PBRN. These studies, however, are limited by their observational design, small sample sizes, and inability to make conclusions regarding the association of initiation format on immunization status beyond 8 months of age. The current proposal addresses these limitations by using an RCT design to test the PIVOT with MI intervention on immunization status at 19 months of age.

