At the conclusion of the video module window, providers will be asked to attend a 90 minute interactive in-person training session led by study staff. Attendance will be required for MOC Part 4 credit. This baseline training session will involve a baseline assessment of provider skills with the communication techniques introduced in the module and teaching and reinforcement of the PIVOT with MI strategy using modeling, role-playing and coaching by the study team. Providers will also receive instructions on how to use the reference sheets developed in Aim 1. Each intervention practice will have its own in-person training session. For PSPRN practices, sessions will be led by [name], [name], [name], and [name]. For COCONet practices, sessions will be led by [name], [name], and [name]. Based on our previous work, provider participation rate in this baseline training is expected to be $\geq 70\%$ (see *C.1.b.* and *C.1.d.*). The intervention period will commence at the conclusion of this baseline training and last 36 months (constituting the 18 month parent recruitment period [see *C.6.k.*] and the 18 months after this period to allow for the last enrolled newborn to reach 19 months old).

Six months into the intervention period, providers will receive a 60 minute in-person refresher training led by the same study team members. This will take a similar format to the initial training but will start with providers sharing their experiences with the PIVOT with MI intervention over the prior 6 months, with demonstrations from each provider of a difficult vaccine conversation with feedback from the MI trainer. At 12 months into the intervention period, we will have a second 90 minute in-person refresher training that will also include viewing 3-5 selected videotaped encounters of 2, 4 and/or 6 month health supervision visits involving intervention providers (with their permission) from the preceding 12 months (see *C.6.g.*) to illustrate “dos and don’ts” of the PIVOT with MI strategy. We will ask providers at the refresher training what they thought went well and what could be improved after watching each videotape. Study champions (1 per practice) will support the PIVOT with MI strategy throughout the remainder of the intervention period by soliciting periodic feedback from providers on use of the intervention and addressing implementation issues with the study team.

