C.6.h. Blinding: Given our intervention, it is not possible to blind providers or investigators to study-arm allocation. However, our analysts will be blinded to study-arm allocation. We will also minimize selection bias by including all parents whose newborns receive health supervision at participating practices in the study and analysis. We will minimize participant bias by blinding providers to PACV-SF scores of parents and parent ascertainment bias by masking the PACV-SF during enrollment by embedding it in a larger survey.

C.6.i. Primary Study Outcome: Our primary outcome will be the immunization status of children of VHPs at 19 months, 0 days of age expressed as the mean percentage of days under-immunized from birth to 19 months for 22 doses of 8 vaccines recommended during this interval (3 Hepatitis B, 3 Rotavirus, 4 Diphtheria, tetanus, and acellular pertussis [DTaP], 3 *Haemophilus influenzae*, type b [Hib], 4 Pneumococcal conjugate, 3 Inactivated poliovirus [IPV], 1 Measles, mumps, rubella [MMR], and 1 Varicella). To calculate the mean percentage of days under-immunized, we will sum the days late for each dose and divide this by the maximum number of days a child could be late if they had received none of the total 22 doses for the 8 vaccines by 19 months. We have chosen to use the mean percentage of days under-immunized because it is a sensitive measure of under-immunization by accounting for missed vaccines doses and delay in receipt of vaccines.¹¹⁷ We have successfully used this measure in previous studies (see C.1.a. and C.1.c.). We will obtain immunization data from WAIIS and CIIS as described in C.6.e.4. As an exploratory secondary outcome, we will also measure the immunization status of children of non-VHPs (expressed as the mean percentage of days under-immunized) since the PIVOT with MI intervention involves use of the presumptive format with all patients and therefore has the potential to also impact the vaccine behavior of non-VHPs.

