For our fidelity study (Aim 2a), we will use conversation analysis (CA) to analyze use of the presumptive format to initiate the vaccine recommendation in videotaped data and the Motivational Interviewing Treatment Integrity (MITI) 4 system¹¹⁹ to assess MI fidelity. CA is the same analytic technique we have used in our preliminary work (see C.1.c.) and searches for patterns in the provider-parent interaction in which a behavior is systematically used to accomplish a social action either vocally or nonvocally.¹²⁰ MITI utilizes a 5-point Likert type scale to assess four MI dimensions (cultivating change talk, softening sustain talk, partnership, and empathy) and tallies 10 specific practitioner behaviors (questions, reflection, persuade with permission, giving information, affirm, emphasize autonomy, seek collaboration, persuade and confront). Summary scores include: (1) reflection to question ratio, (2) percentage of complex to simple reflections, and (3) percent of MI adherent statements.

[name] will utilize a subset of the videotaped encounters to develop a coding scheme for the PIVOT with MI communication practices. [name] and [name] will teleconference weekly with [name] during this analysis to review identified communication patterns and their correlation to the PIVOT with MI intervention. After completion of the coding scheme, [name] will then train multiple coders from the study team on the coding scheme using 10% of the videotaped data. We will measure inter-rater reliability between the coders using up to an additional 20% of the data until κ scores reach a minimum of .70. Coders will then continue to independently code all remaining data (and recode the initial 10% of training data). All discrepancies in coding between the coders will be resolved through discussion with [name].

C.6.k. Sample Sizes/Power Calculations: Based on preliminary data (see C.1.a.), children of VHPs had a mean percentage of days under-immunized of 26.2% (standard deviation [SD] 29.8) from birth to 19 months of

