age for 6 vaccines combined (Hepatitis B, DTaP, Hib, IPV, MMR, and Varicella).¹⁸ This corresponds to an average of 37 days late per vaccine dose. To be able to detect with adequate power ($\geq 90\%$) a decrease in under-immunization of 10 days—a decrease that has the potential to be clinically meaningful since 27 days would not be considered late for most vaccines because of the 30 day window in which most vaccine doses are recommended¹²¹—we need to enroll 600 VHP/newborn pairs total, with 300 per arm and 25 at each of the 24 study practices (assuming an α of 0.05, a SD of 20, and an intraclass correlation coefficient for within-clinic correlation of 0.02²⁸). Assuming a 10% prevalence of VHPs (see C.1.b),²⁸ we will need to approach 6,000 parents to reach our sample size goal. This is feasible to achieve in our designated 18 month recruitment period given our design to integrate PACV-SF screening of parents of newborns into standard practice workflow and our estimate (determined by spot chart reviews at PSPRN and COCONet practices) that there are ≥ 10 newborns per clinic per week in PSPRN and COCONet practices. If we vary our assumptions regarding VHP prevalence (7.5%) or SD (25), we would need to approach 8,000 and 12,000 parents, respectively, for adequate ($\geq 90\%$) power to detect the same effect size, both of which remain feasible within the 18 month enrollment period assuming ≥ 10 newborns per clinic per week. If we have unbalanced enrollment across study arms (i.e. not 1:1 enrollment in intervention and control arms), we will continue enrollment beyond 600 VHP/newborn pairs total in order to reach at least 300 VHP/newborn pairs per arm given the impact of an imbalance on our power.

For our fidelity outcome (Aim 2a), power can be considered in terms of the number of videotaped interactions needed to develop this coding scheme. Based on our prior studies (see C.1.c.), 3 videotaped visits per provider should be adequate to achieve sufficient behavioral variation across providers. We will therefore videotape up to 360 encounters (up to 180 in each state), which averages to 3 videotaped encounters per practice provider.

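### The 37 days late per dose in C.6.k does not follow from the C.6.i outcome rule, so the 10-day target and its 30-day-window rationale cannot both stand as written

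*Combined protocol and SAP*

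**What the plan says.** C.6.i defines the primary outcome per dose: "we will sum the days late for each dose and divide this by the maximum number of days a child could be late", the maximum being that of a child who received none of the 22 doses by 19 months. C.6.j models the outcome as a percentage.

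C.6.k starts from pilot data on six vaccines, in which "children of VHPs had a mean percentage of days under-immunized of 26.2"%, with an SD of 29.8. It continues: "This corresponds to an average of 37 days late per vaccine dose". The target is a decrease of 10 days, from 37 to 27, called potentially meaningful because "27 days would not be considered late for most vaccines because of the 30 day window". The sample size is 600 pairs (24 practices of 25), with alpha 0.05, an SD of 20 with no unit, an ICC of 0.02 and at least 90% power. For an SD of 25, C.6.k gives 12,000 parents approached (1,200 pairs at 10% prevalence) for "power to detect the same effect size, both of which remain feasible".

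The protocol contains no table of dose due ages and no lateness cut-offs. On timing it mentions a hepatitis B birth dose (Table 1 footnote: "Only delay of the birth dose of the hepatitis B vaccine would be relevant for parents of children") and health supervision visits at 2, 4 and 6 months (C.1.c: "2, 4, and 6 month visits, we asked parents what format"; C.6.f: "selected videotaped encounters of 2, 4 and/or 6 month health supervision visits").

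**The concern.** The outcome is analysed in percent, but the only stated target is in days. The link between the two is the single figure of 37 days, given without derivation. That figure looks too small for a per-dose sum. Many of the doses belong to series that start in the first months of life, and each such dose could be late for well over a year by 19 months.

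Two things rest on the conversion. One is what the trial can detect in days per dose, and hence how a null result may be read against a 10-day benefit. The other is the only reason C.6.k gives for clinical relevance, namely that the target mean falls inside a 30-day window.

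**Working it through.** **1. Reproduce the stated power.** Inputs from C.6.k: 300 per arm, 25 per practice, ICC 0.02, SD 20, alpha 0.05 (two-sided assumed).

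- Design effect = 1 + 24 × 0.02 = 1.48. SE = 20 × √(2 × 1.48/300) = 1.987.
- Effect 10 and SD 20 in the same unit: power 99.9%, and 192 pairs would suffice for 90% (normal). That is not the stated plan.
- Effect in percentage points by C.6.k's own ratio (inferred): 10/37 × 26.2 = 7.08. Power is 94.6% (normal) or 92.6% (t, 22 df).
- SD 25 with 1,200 pairs (50 per practice): SE = 2.031, power 93.7% or 91.5%.

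So the stated power reproduces when the effect is read as about 7.1 percentage points and the SD of 20 as percentage points. The difference detectable with 90% power is 3.2415 × 1.987 = 6.44 points (t: 6.74). This depends on SD, N and ICC, not on the 37.

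**2. What 37 days implies under C.6.i.** Average maximum per dose = 37/0.262 = 141.2 days. With 19 months = 578.3 days, the average dose would become late at 578.3 − 141.2 = 437.1 days, or 14.4 months.

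**3. Per-dose count under assumed due ages.** These assumptions serve the arithmetic only: doses 1 and 2 of DTaP, Hib and IPV due at 2 and 4 months; hepatitis B dose 1 at birth; a 30-day window; 15 doses for the six vaccines (C.6.i counts; C.6.k gives none for the pilot). These seven doses alone give 548.3 + 3 × 487.4 + 3 × 426.6 = 3,290 days. The other eight doses are then varied. Power for 10 days is Φ(Δ/1.987 − 1.96), where Δ is 10 days as a percentage of the maximum per dose.

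| Other 8 doses late from | Max per dose | 26.2% | 6.44 points | 10 days in points | Power for 10 days (t) |
|---|---|---|---|---|---|
| 19 months (zero days) | 219 | 57 d | 14 d | 4.56 | 63% (59%) |
| 16 months | 268 | 70 d | 17 d | 3.73 | 47% (43%) |
| 13 months | 317 | 83 d | 20 d | 3.16 | 36% (33%) |
| 10 months | 365 | 96 d | 24 d | 2.74 | 28% (26%) |

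The first row is a floor, because it gives eight doses no possible late days. The planned target mean of 26.2 − 7.1 = 19.1% is 42 days in the first row and 70 in the last.

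Sensitivity of the floor: due ages of 4 and 8 months with a 60-day window give 2,532/15 = 169 days per dose. Then 26.2% = 44 days, 6.44 points = 10.9 days, and power for 10 days is at most 85% (t: 81%). The mismatch shrinks but remains.

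For the trial's 22 doses, with rotavirus and pneumococcal doses 1 and 2 also assumed due at 2 and 4 months: 548.3 + 5 × 487.4 + 5 × 426.6 = 5,118; /22 = 233 days per dose at least, so 6.44 points is at least 15 days.

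**4. Once-per-vaccine count, divided by doses.** Hepatitis B late from 30 days; DTaP, Hib and IPV from 2 months plus 30 days; MMR and varicella assumed late from 16 or 17 months. Total 548.3 + 3 × 487.4 + 2 × 91.3 (or 60.9) = 2,193 (or 2,132). Divided by 15: 146.2 (or 142.2) days. Times 0.262: 38.3 (or 37.2) days, close to the stated 37. On this rule 10 days is 6.8 to 7.0 points, with power 93 to 94% (t: 91 to 92%).

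**5. SD.** All of the above takes the SD of 20 as given. At the quoted 29.8, 7.08 points with 600 pairs has SE 2.960 and power 67% (t: 63%).

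**The case against.** The strongest reply is that 37 days can be reproduced. A once-per-vaccine count spread over 15 doses gives 37 to 38 days, and 10 days is then adequately powered. The actual derivation may lie in the cited pilot work. The figure may therefore be loosely worded rather than miscalculated. This stands, and it rules out calling the 37 a proven arithmetic error. It does not rescue the text: C.6.i counts each dose, and a vaccine-level total divided by the number of doses is not how late a dose is, so 27 cannot be set against a per-dose window.

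A reader might infer that the detectable effect simply is 14 to 24 days rather than 10. The documents do not support that, because the range rests on due ages and pilot dose counts that they do not state, and on the per-dose reading. Fuller assumed schedules gave about 19 to 27 days, which shows how far the figure depends on these inputs.

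A reader might also infer, in the other direction, that the sample size has been cleared. It has not. The 7.1 points come from the disputed 37 and use an SD of 20 against a quoted 29.8.

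Finally, the consequence is limited. The analysis is in percent, so the estimand, model and estimate are untouched, and a null result would be judged first by its confidence interval in percentage points.

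**Conclusion.** The conversion in C.6.k does not follow from the outcome rule in C.6.i. On that rule 37 days requires a maximum of 141 days per dose. Under the assumed 2- and 4-month due ages with a 30-day window the maximum is at least 219.

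On either counting rule, something C.6.k relies on fails:

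- **Per dose:** under those due ages, power for a true 10 days is at most about 63%, not at least 90%. The detectable effect is at least 14 days, or about 17 to 24 days if the other eight doses become late from 16 to 10 months on average. The target mean of at least 42 days lies outside the 30-day window.
- **Per vaccine, divided by doses:** the power holds, but 37 and 27 are not the lateness of a dose, so the window comparison does not apply.

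Confidence is high that the conversion is undefined and at odds with C.6.i as written. It is moderate for the size in days, which depends on the assumed due ages, window and dose counts. This point neither confirms nor refutes that 600 pairs are enough.

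**What to change.** In C.6.k:

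1. State the target difference and the SD in percentage points, the scale analysed in C.6.j. If about 7 points was intended, say so.
2. State the counting rule behind 37 days (per dose or per vaccine), the lateness cut-offs, whether the 30-day window is already subtracted, and whether the pilot 26.2% used the C.6.i formula.
3. Compute the maximum days late for the 15-dose and 22-dose sets under C.6.i with the due dates the study will use.
4. Restate the detectable effect in days per dose, or the power for 10 days per dose.
5. Reconcile the 30-day-window rationale with the rule used.

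The cost is a short recalculation and a few sentences. The detectable effect in days may look less favourable and the clinical rationale may need rewording. The outcome and the model do not change.

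### Section C.6.k claims at least 90% power using an unexplained SD of 20, although its own preliminary data give 29.8, at which 600 pairs have about 63–67% power

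*Combined protocol and SAP*

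**What the plan says.** Section C.6.k starts from preliminary data in which "children of VHPs had a mean percentage of days under-immunized of 26.2% (standard deviation [SD] 29.8"), measured from birth to 19 months "for 6 vaccines combined (Hepatitis B, DTaP, Hib, IPV, MMR, and Varicella"). It converts the mean to days: "This corresponds to an average of 37 days late per vaccine dose". The target is a fall of 10 days, to 27, which the section calls potentially meaningful because 27 days lies inside the 30-day window for most doses.

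For at least 90% power, the section states that "we need to enroll 600 VHP/newborn pairs total, with 300 per arm and 25 at each of the 24 study practices", with α 0.05, "a SD of 20, and an intraclass correlation coefficient for within-clinic correlation" of 0.02. The ICC carries a citation; the SD of 20 does not.

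The section then tests its assumptions: "If we vary our assumptions regarding VHP prevalence (7.5%) or SD (25"), arriving at 8,000 and 12,000 parents to approach, "both of which remain feasible within the 18 month enrollment period assuming" at least 10 newborns per clinic per week. No case uses an SD of 29.8.

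Section C.6.i defines the primary outcome as the "mean percentage of days under-immunized from birth to 19 months for 22 doses of 8 vaccines recommended during this interval". The documents report no SD for that 8-vaccine measure.

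**The concern.** The section takes the mean of the preliminary data to set its 37-day starting point, then sets aside the SD of the same data without comment. An SD of 20 is 33% below 29.8 (1 − 20/29.8), and the variance is 55% below (1 − (20/29.8)²). The sensitivity case of 25 makes the calculation look stress-tested but stops short of the value reported a few lines earlier.

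At least 90% power is the stated reason for 600 pairs. A reader who trusts it would treat a null result as fairly strong evidence against a 10-day effect. If the true SD is near 29.8, a null result is much weaker evidence.

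**Working it through.** **Inputs (C.6.k unless noted).** Preliminary mean 26.2% and SD 29.8 pp; 37 days per dose equated with 26.2%; target 10 days; ICC 0.02; 24 practices of 25, so 300 per arm; α 0.05, taken as two-sided because the section does not say. VHP prevalence is 10%. The section states no inflation for dropout, and none is applied.

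**Effect in percentage points.** 10/37 × 26.2 = 7.08 pp.

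**Formulas.** With m pairs per practice and 12 practices per arm, the design effect is 1 + (m − 1) × 0.02 and SE = SD × √(2 × design effect / (12m)). At m = 25 the design effect is 1.48 and SE = SD × √(2 × 1.48/300). Power is Φ(7.08/SE − 1.96) under the normal approximation. A noncentral t with 24 − 2 = 22 df is shown as a small-sample variant; the plan itself names no degrees of freedom.

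**The plan's figure first, then the other SDs (600 pairs).**

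| SD (pp) | SE | 7.08/SE | Power, normal | Power, t (22 df) |
|---|---|---|---|---|
| 20 | 1.987 | 3.56 | 94.6% | 92.6% |
| 25 | 2.483 | 2.85 | 81.4% | 77.8% |
| 29.8 | 2.960 | 2.39 | 66.7% | 62.8% |

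The stated figure of at least 90% reproduces at SD 20 pp.

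**Unit of the SD.** In the SD 25 case, 12,000 parents at 10% prevalence means 1,200 pairs, or 50 per practice (design effect 1.98). With SD 25 pp, power is 93.7% (normal) or 91.5% (t), so that case reproduces too. Read in days, an SD of 25 against a 10-day effect would already give 98.1% or 97.0% with 600 pairs, and there would be no reason to double enrolment. Percentage points is therefore the reading that fits both cases, and it is the scale of the 29.8.

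**Largest SD that keeps 90% power with 600 pairs.** 22.0 pp (normal) or 21.0 pp (t).

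**Detectable effect at SD 29.8 with 90% power and 600 pairs.** 9.6 pp (normal) or 10.0 pp (t). Multiplied by 37/26.2, these are 13.6 or 14.2 days, against the 10-day target.

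**Enrolment for 90% power at SD 29.8.** The smallest whole number per practice is 81 (normal) or 104 (t), which is 1,944 or 2,496 pairs, or 19,440 or 24,960 parents at 10% prevalence. The stated minimum newborn rate gives 24 × 10 × 78 weeks = 18,720 newborns if every parent is screened, so 1,872 VHPs (78 per practice). Power there is 89.7% (normal) or 86.9% (t).

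**Sensitivity to the day-to-pp conversion.** The 7.08 pp comes from a 6-vaccine conversion. If 10 days were 6 to 8 pp on the 8-vaccine measure (an assumed range), power with 600 pairs is 49–77% at SD 29.8 and 82–98% at SD 20 (lower end t at 6 pp, upper end normal at 8 pp).

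**The case against.** The strongest reply is that 29.8 is not the SD of the trial's outcome. It describes 6 vaccines rather than 8, C.6.k does not give the hesitancy cut-off behind it, and the conversion of 26.2% to 37 days cannot be checked from the documents. This stands as a limit on the figure of 63–67%. It does not support 20, because the documents give no SD for the 8-vaccine measure and C.6.k does not offer the change of measure as its reason.

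A second reply is that an equal, unadjusted SD in both arms is pessimistic. If the SD fell in proportion to the mean (an assumption), the intervention-arm SD would be 29.8 × (26.2 − 7.08)/26.2 = 21.7 and power 78% (normal) or 74% (t). If covariates explained 10–30% of the variance (also assumed), power would be 71–82% (normal) or 67–78% (t). Neither reaches 90%: getting from 29.8 down to 21–22 pp by adjustment would require covariates to explain about 45–50% of the variance. A smaller ICC does not rescue the claim either, since even at ICC 0 an SD of 29.8 gives 83% (normal) or 79% (t).

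Third, the 10-day target has a clinical argument, and only its 37-day start comes from the preliminary data. That is correct and does not change the power.

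Fourth, the feasibility statement covers only the cases the section names, the newborn rate is a minimum, and the shortfall at that minimum is only 0.3 to 3 points. That is fair. The feasibility text is not wrong; it just does not extend to an SD of 29.8.

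**Conclusion.** The concern holds. The calculation in C.6.k is arithmetically correct, but its SD is unsupported and lies well below the only SD the section reports for percentage of days under-immunized. At SD 29.8, 600 pairs give about 63–67% power for the 10-day target, and the claim of at least 90% requires an SD of at most about 21–22 pp.

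These figures assume a two-sided α of 0.05, ICC 0.02, equal practice sizes, equal SDs in the two arms, no covariate gain, and the section's own 6-vaccine conversion from days to percentage points. They are a scenario at the closest available SD, not the trial's known power. The absence of a stated basis for SD 20 does not depend on any of these assumptions. The effect estimate, its interval and the type I error are unaffected. This should be fixed.

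**What to change.** In C.6.k, give the SD its unit (percentage points) and add a statement such as: at the preliminary SD of 29.8 pp (6-vaccine measure, the closest available estimate for the 8-vaccine outcome), 600 pairs give about 63–67% power for a 7.1 pp (10-day) reduction, and at least 90% holds only if the SD is at most about 21–22 pp.

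Keep SD 20 and 25 as scenarios, labelled as lying below the preliminary SD. If there is a basis for 20, state it as well; a stated basis alone would still leave the reader without the power at 29.8. Note that the day-to-percentage-point conversion comes from the 6-vaccine measure.

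The cost is wording and a less favourable power figure. Enrolment and the analysis do not change.
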